In collaboration with Oregon Health and Science University (OHSU), the FHCRC has conducted a study to determine the optimum dose of treosulfan, in combination with fludarabine prior to allogeneic HCT with traditional donors in patients with AML, ALL, or MDS. "Optimal" dose was determined by safety and efficacy, as defined by incidence of severe/fatal RRT, graft

failure and TRM. Thirty-six patients (8 children and 28 adults > 18 years), with a median of 41 (5-58) years, and diagnosed with AML in first (n=19), second remission (n=7) or not in remission (n=4), ALL in second remission (n=2) or MDS (n=4) have been treated. Patients were considered to be at high risk for TRM because of aggressive therapy for a prior malignancy, comorbid conditions or previous HCT. Patients received Treosulfan at 12 (n=5) or 14 g/m²/day (n=31) on days -6 to -4, and Fludarabine (30 mg/kg/day) on days -6 to -2. GVHD prophylaxis was with tacrolimus and methotrexate (n=35) or cyclosporine and methotrexate (n=1). Donors were HLA-matched siblings (n=19) or unrelated volunteers (n=17); source of stem cells were bone marrow (n=7) or filgrastim-mobilized peripheral blood cells (n=29). Neutrophil engraftment occurred at a median of 18 (11-30) days. Grade II-IV acute graft-versus-host disease (GVHD) was observed in 9 of 36 patients, and chronic GVHD in 8 of 23 evaluable patients surviving beyond post-transplant day 80. Dose-limiting RRT was observed in 1 of 36 patients (mucositis requiring intubation). With a median follow-up of 118 (20-575) days, estimated one-year overall and disease-free survival, relapse and TRM are 83%, 78%, 22% and 0%, respectively. Day-100 mortality observed to date is 6%. Treosulfan/Fludarabine seems to be a well-tolerated regimen with promising disease control and low rates of RRT and TRM in patients with acute leukemia and MDS.

Treosulfan in cord transplant

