| 
 • Infection (bacterial/fungal/viral) • Lowering all blood counts leading to anemia, increased risk for infections and bleeding • Mucositis (inflammation lining of mouth which may be painful) • Diarrhea, nausea, vomiting • Abdominal pain • Fever (often associated with very low white blood count) • Increased bilirubin** • Fatigue/lethargy** • Itching skin* | 
 • Rash • Alopecia (temporary hair loss) • Elevated liver function tests • Dysphagia (difficult swallowing) • Decreased appetite** • Insomnia** • Headache/dizzy** • Heart rhythm abnormalities** • High blood pressure** • Shortness of breath** • Gastritis/constipation** • Generalized pain (muscles and bone)** • Abnormal kidney function** | 
 • High blood glucose** • Confusion** • Peripheral neuropathy** • Low blood pressure** • Pneumonitis** • Severe skin rash with blisters and sloughing of skin** • Dry mouth** • Severe liver function abnormality** | 
 • Acidosis, electrolyte abnormalities • Liver failure/severe liver toxicity • Dry eyes • Kidney failure • Heart failure** • Muscle weakness** • Encephalopathy** • High or Low blood pressure* |
|--|--|---|---|

* Risks unique to Pediatric Patients

**Risks unique to Adult Patients

There have been isolated reports of seizure in infants (4 months of age or less) after receiving treosulfan combined with fludarabine as in this study or with cyclophosphamide (another chemotherapy drug that is not being used in this study). Very young children will be very closely watched for signs of neurologic side effects.

Fludarabine

| Common 21-100 people out of 100 | Less Frequent 5-20 people out of 100 | Uncommon <5 people out of 100 |
|--|---|---|
| 
Severe suppression of blood counts
 
Diarrhea
 
Anorexia
 
Mucositis
 
Nausea/vomiting
 
Stomatitis
 
Osteoporosis
 
Dysuria
 | 
Chills
 
Fever
 
GI bleeding
 
Peripheral edema
 | 
Neurotoxicity
 
Agitation and confusion
 
Blurred vision
 
Peripheral neuropathy
 
Hearing loss
 
Headache
 
Cerebellar syndrome
 
Blindness
 
Coma
 
Weakness
 
Depression
 
Insomnia
 
Hemorrhagic cystitis (except in FA)
 
Abnormal renal function test
 
Autoimmune hemolytic anemia
 
Deep venous thrombosis
 
Aneurysms
 |

| | | |
|--|--|---|

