Grade 3 or 4 adverse events (or highly unusual grade 2 adverse events) and all SAEs, which occur from the start of study treatment (pre-transplant conditioning) through Day +100 post transplant will be assessed by the investigator or qualified designee and recorded on the Case Report Form (CRF). Clinically significant AEs beyond Day 100 may also be captured at the discretion of the investigator. When a subject experiences relapse or graft failure and goes on to further treatment off protocol, adverse events will no longer be collected with the exception of death. The investigator should attempt to establish a diagnosis of the event on the basis of signs, symptoms and/or other clinical information. In such cases, the diagnosis should be documented as the adverse event and/or serious adverse event and not described as the individual signs or symptoms. The following information should be recorded:

- Description of the adverse event using concise medical terminology
- Description as to whether or not the adverse event is serious
- The start date (date of adverse event onset)
- The maximum severity (grade) of the adverse event
- A description of the potential relatedness of the adverse event to study drug or a study procedure

3) Grading of the severity of an Adverse Event

All AEs will be graded in severity according to the modified (for HSCT) NCI Common Toxicity Criteria for Adverse Events (CTCAE) Version 3.0 Appendix IX (https://ctep.cancer.gov/protocoldevelopment/electronic_applications/docs/ctcaev3.pdf). If a CTCAE criterion does not exist, the investigator should use the grade or adjectives: Grade 1 (mild), Grade 2 (moderate), Grade 3 (severe), Grade 4 (life-threatening), or Grade 5 (fatal) to describe the maximum intensity of the adverse event.

4) Attribution of Adverse Event

Association or relatedness to the study agent will be assessed by the investigator as follows:

- Definite: The event follows a reasonable temporal sequence from exposure to the investigational agent, has been previously described in association with the investigational agent, and cannot reasonably be attributed to other factors such as the patient's clinical state, other therapeutic interventions or concomitant medications; AND the event disappears or improves with withdrawal of the investigational agent and/or reappears on re-exposure (e.g., in the event of an infusion reaction).

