| Ascites (none-malignant) | Symptomatic, requiring therapeutic paracentesis | Life-threatening physiologic Consequences |
| Colitis Also consider Hemorrhage/ bleeding with grade 3 or 4 thrombocytopenia, hemorrhage/bleeding without grade 3 or 4 thrombocytopenia, melaena/GI bleeding, rectal bleeding/hematochezia, hypotension. | Abdominal pain, fever, change in bowel habits with ileus or peritoneal signs, and radiographic or biopsy documentation | Perforation or requiring surgery or toxic megacolon |
| Diarrhea associated with graft versus host disease (GVHD) for BMT studies, if specified in the protocol. For pediatric BMT studies, if specified in the protocol. Also consider Hemorrhage/ bleeding with grade 3 or 4 thrombocytopenia, hemorrhage/bleeding without grade 3 or 4 thrombocytopenia, pain, dehydration, hypotension. | >1500mL of diarrhea/day >15mL/kg of diarrhea/day | Severe abdominal pain with or without ileus |
| Duodenal ulcer (requires radiographic or endoscopic documentation) | Uncontrolled by outpatient medical management; requiring hospitalization | Perforation or bleeding, requiring emergency surgery |
| Gastric ulcer (requires radiographic or endoscopic documentation) Also consider Hemorrhage/bleeding with grade 3 or 4 thrombocytopenia, hemorrhage/bleeding without grade 3 or 4 thrombocytopenia. | Bleeding without perforation, uncontrolled by outpatient medical management; requiring hospitalization or surgery | Perforation or bleeding, requiring emergency surgery |
| Gastritis Also consider Hemorrhage/bleeding with grade 3 or 4 thrombocytopenia, hemorrhage/bleeding without grade 3 or 4 thrombocytopenia. | Uncontrolled by out-patient medical management; requiring hospitalization or surgery | Life-threatening bleeding, requiring emergency surgery |
| Pancreatitis Also consider Hypotension. | Abdominal pain with pancreatic enzyme elevation | Complicated by shock (acute circulatory failure) |

2275.00

| | | |
|--|---|--|
| 
Note: Amylase is graded in the METABOLIC/LABORATORY category.
 
Mucositis
 
Note: Radiation-related mucositis is graded as Mucositis due to radiation.
 | | |

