| 
Typhlitis (inflammation of the cecum)
 
Also consider Hemorrhage/bleeding with grade 3 or 4 thrombocytopenia, hemorrhage/bleeding without grade 3 or 4 thrombocytopenia, hypotension, febrile neutropenia.
 | 
Painless erythema, edema, or ulcers preventing swallowing or requiring hydration or parenteral (or enteral) nutritional support
 
Abdominal pain, diarrhea, fever, and radiographic or biopsy documentation
 | 
Severe ulceration requiring prophylactic intubation or resulting in documented aspiration pneumonia
 
Perforation, bleeding or necrosis or other life-threatening complication requiring surgical intervention (e.g., colostomy)
 |

HEMORRHAGE

Notes:

Transfusion in this section refers to pRBC infusion.

For any bleeding with grade 3 or 4 platelets (<50,000), always grade Hemorrhage/bleeding with grade 3 or 4 thrombocytopenia. Also consider Platelets, Transfusion: pRBCs, and Transfusion: platelets in addition to grading severity by grading the site or type of bleeding.

If the site or type of Hemorrhage/bleeding is listed, also use the grading that incorporates the site of bleeding: NS Hemorrhage/bleeding, Hematuria, Hematemesis, Hemoptysis, Hemorrhage/bleeding with surgery, Melena/lower GI bleeding, Petechiae/purpura (Hemorrhage/bleeding into skin), Rectal bleeding/ hematochezia, Vaginal bleeding.

| Adverse Event | Grade 3 | Grade 4 |
|--|--|---|
| Hemorrhage/bleeding with grade 3 or 4 thrombocytopenia | Requiring transfusion | Catastrophic bleeding, requiring major non-elective intervention |
| Also consider Platelets, hemoglobin, transfusion: platelets, transfusion: pRBCs, site or type of bleeding. | | |
| If the site is not listed, grade as Hemorrhage – Other (specify site): _____ | | |
| Note: This adverse event must be graded for any bleeding with grade 3 or 4 thrombocytopenia. | | |
| CNS hemorrhage/bleeding | Bleeding noted on CT or other scan with no clinical consequences | Hemorrhagic stroke or hemorrhagic vascular event (CVA) with neurologic signs and symptoms |
| Hemoptysis | Requiring transfusion | Catastrophic bleeding, requiring major non-elective intervention |
| Melena/GI bleeding | Requiring transfusion | Catastrophic bleeding, requiring major non-elective intervention |
| Rectal bleeding/hematochezia | Requiring transfusion | Catastrophic bleeding, requiring major non-elective intervention |

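### The Appendix IX grade 3 mucositis criterion says painless, so painful mucositis that stops swallowing may go unrecorded or be graded inconsistently

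*Combined protocol and SAP*

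**What the plan says.** Appendix IX of the protocol lists only grades 3 and 4. For mucositis:

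- Grade 3 opens with "Painless erythema, edema, or ulcers preventing swallowing"; the full entry is "Painless erythema, edema, or ulcers preventing swallowing or requiring hydration or parenteral (or enteral) nutritional support".
- Grade 4: "Severe ulceration requiring prophylactic intubation or resulting in documented aspiration pneumonia".
- A note under the mucositis label adds: "Radiation-related mucositis is graded as Mucositis due to radiation".

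Section 12.B.3 grades all adverse events on the modified toxicity scale in Appendix IX and links version 3.0 of the NCI criteria as its parent. Where no criterion exists, it lets the investigator use an adjectival grade, with severe as grade 3.

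Section 12.B.2 sets what goes on the CRF from the start of conditioning to day +100: "Grade 3 or 4 adverse events (or highly unusual grade 2 adverse events) and all SAEs". Section 12.B.1.b states that hospitalizations of the kind common in transplant, including those for gastrointestinal toxicity, are not recorded as SAEs.

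The treosulfan table in Section 10.A.1 places this entry in its most frequent column (above 10%): "Mucositis (inflammation lining of mouth which may be painful".

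**The concern.** The grade 3 criterion describes lesions bad enough to stop swallowing or to require fluids or feeding support, yet it opens with the word painless. Section 10.A.1 says that the same toxicity can be painful. Appendix IX itself, in its erythema multiforme row, gives stomatitis with pain as an example of grade 3.

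This is an operative recording criterion, not background text. Because the CRF threshold is essentially grade 3, a patient who falls outside the grade 3 wording tends to fall outside the safety data. Mucositis also matters for this regimen: Section 10.A.1 lists it for treosulfan, for fludarabine (21 to 100 per 100 patients) and for total body irradiation (TBI; 5 to 20 per 100), and Section 2 argues for the regimen partly on reduced toxicity. At stake is whether its severe mucositis is tabulated completely and in the same way at every site.

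**Working it through.** The plan states no figure to reproduce, so the check sets the passages side by side.

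**1. Does the wording belong to mucositis?** The row is broken in the machine-read text, and the criterion appears beside the typhlitis label. Typhlitis has its own grade 3 text in the same merged cell, "Abdominal pain, diarrhea, fever, and radiographic or biopsy documentation", and its own grade 4 text on perforation, bleeding or necrosis. The swallowing criterion therefore belongs to mucositis, whose label comes just before.

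**2. What grade does each presentation receive?** The grade 3 sentence can be read in three ways.

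| Presentation | A: painless governs the whole sentence | B: painless governs only erythema | C: fluid or feeding support is a separate limb |
|---|---|---|---|
| Painless ulcers, cannot swallow | 3 | 3 | 3 |
| Painful ulcers, cannot swallow, no support needed | none | 3 | none |
| Painful ulcers, needs feeding support | none | 3 | 3 |
| Severe ulceration with prophylactic intubation | 4 | 4 | 4 |

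The two middle rows change with the reading. Two sites could grade the same patient differently, and on reading A both painful presentations short of grade 4 have no grade.

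**3. Do the other capture routes close the gap?**

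- *Highly unusual grade 2 event:* a toxicity listed above 10% hardly qualifies.
- *SAE by hospitalization:* Section 12.B.1.b excludes the common transplant-related gastrointestinal admissions. The life-threatening and important-medical-event routes remain, but would catch only some cases.
- *Adjectival grade:* Section 12.B.3 offers it when a criterion does not exist. A mucositis criterion does exist, so its use here is arguable.

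None of these is reliable.

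**4. The radiation note.** The regimen includes TBI on day -1. The note sends radiation-related mucositis to a separate item, and no row for that item appears in Appendix IX as read.

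**5. Can the shortfall be sized?** Section 2 reports grade 3 mucositis in two earlier series:

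- Treosulfan/cyclophosphamide: 4/27 = 14.8%; 130 × 4/27 = 19.3.
- Treosulfan/fludarabine: 2/56 = 3.6%; 130 × 2/56 = 4.6.

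If these rates applied to the planned 130 patients, about 5 to 19 grade 3 cases would be expected. The shortfall would be that number times the fraction both painful and left ungraded. The documents give no value for that fraction. With a range of 0 to 1, the product runs from 0 to about 19 and is not an estimate. The upper end comes from a different drug combination, neither series is described as including TBI, and both used marrow or peripheral blood rather than cord blood.

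**6. Which analyses use the grade?** The primary endpoints in Section 3.A are graft failure and day-200 NRM. The Section 14 stopping rule counts NRM events. Mucositis is not among the secondary endpoints in Section 3.B or Section 14, and Section 14 specifies no toxicity-rate estimate or test.

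**The case against.** The best defence is that the entry is workable despite the word. An investigator may take it as a slip and assign grade 3. Readings B and C are grammatically available, and under C any mucositis needing parenteral nutrition is grade 3 whatever the pain. The parent scale is linked, and an investigator who finds that the entry does not fit may use the adjectival grade. The Section 10.A.1 wording is a plain-language risk description, not a grading rule. Since other words in the machine-read text look corrupted, this one should be confirmed on the page before anyone acts.

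Much of this stands. It defeats any claim that painful mucositis certainly receives no grade. It does not remove the point: several tenable readings that give different grades are a defect in a recording criterion, and the fallback does not clearly apply where an entry exists.

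A reader might go further in three ways that the documents do not support.

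- *That mucositis is under-counted in this trial.* No passage shows how any site applied the word or that a case was missed.
- *That 5 to 19 cases will be lost.* The painful and ungraded fraction is unknown, and the source regimens differ.
- *That the dose-limiting event in the US treosulfan/fludarabine study illustrates the gap.* That study reports: "Dose-limiting RRT was observed in 1 of 36 patients (mucositis requiring intubation". A comparable case would most naturally be grade 4 here, which carries no pain qualifier.

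**Conclusion.** The grade 3 mucositis entry is wrong as written. It conflicts with Section 10.A.1 and, read literally, leaves painful mucositis that prevents swallowing without a listed grade unless intubation or aspiration pneumonia follows. The consequence is a risk of incomplete or inconsistent recording, not a demonstrated under-count, and its size cannot be derived from the documents.

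The effect stops at adverse-event tabulation. No primary or secondary endpoint, sample-size argument or stopping boundary depends on it, so this is a minor correction that improves the safety data.

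The conclusion assumes that the word stands on the source page as it does in the extracted text, and that Appendix IX, rather than the linked parent scale, is what sites use when they grade.

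**What to change.** 1. Check the grade 3 mucositis entry against the source page and the parent scale cited in Section 12.B.3. If the word is there, correct the entry so that painful lesions are included, either by replacing the word or by deleting the pain qualifier so that swallowing and fluid or feeding support define the grade. This costs a one-word amendment to Appendix IX.
2. In the same amendment, reconcile the radiation note with the table: either supply the row it refers to or state that mucositis after this TBI-containing regimen is graded in the mucositis row.
3. Ask each site how it has applied the criterion. Section 14 gives 34 + 40 = 74 patients enrolled at the time of writing. If no site applied it literally, nothing more is needed. If any did, the recheck for that site must use source records, because an ungraded case would not be on the CRF. That is a modest added cost, limited to the sites concerned.
4. If past cases cannot be regraded, say in the safety report that grade 3 mucositis before the correction may be incomplete.

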APPENDIX X: FHCRC IRB Policies

<http://extranet.fhcrc.org/EN/sections/iro/irb/policy/index.html>

Appendix XI: Adverse Events Associated or Expected with Hematopoietic Cell Transplantation

1. **Graft versus host disease**: GVHD is a major toxicity associated with the infusion of allogeneic donor stem cells. GVHD may be acute or chronic and may affect multiple organ systems, including the skin, liver, and GI tract.
2. **Opportunistic infections**, including viral and fungal infections, can result in severe pulmonary, neurologic, hepatic and other organ dysfunction, and possible death.
3. **Gastrointestinal toxicity**. Nausea and vomiting can be anticipated during the entire course of ablative therapy. Mucositis and diarrhea should be expected. Prednisone can cause GI bleeding.
4. **Cardiac toxicity**. Cardiotoxicity (congestive heart failure, pericardial effusion, EKG changes) is uncommonly associated with the chemotherapy agents and TBI used in the regimen and these sequelae may prove lethal.
5. **Pulmonary toxicity**. Diffuse interstitial pneumonitis of unknown etiology and diffuse alveolar hemorrhage occur with some regularity after BMT and interstitial fibrosis occurs much more rarely. Both are well-described complications of intensive chemotherapy and TBI regimens and may prove lethal.
6. **Hepatic toxicity**. Veno-occlusive disease of the liver is a common toxicity of high-dose chemoradiotherapy and may result in death. Cyclosporine may cause elevation of ALT/AST.
7. **Renal dysfunction**. Chemoradiotherapy may uncommonly cause renal dysfunction. More commonly, nephrotoxicity results from cyclosporine and generally responds to dose reduction. Rarely, idiopathic or calcineurin inhibitor-associated hemolytic-uremic syndrome may occur and may be progressive and fatal. A syndrome of moderate renal insufficiency and hemolysis has been seen 5-7 months post HSCT after intensive multi-agent conditioning plus TBI.
8. **Hemorrhagic cystitis**, manifested either as gross or microscopic hematuria, is a common toxicity after high-dose chemoradiotherapy, but usually associated with regimens that include cyclophosphamide. Hemorrhagic cystitis may predispose to a long-term increased risk of bladder cancer.
9. **Central nervous system toxicity**. Radiation and chemotherapy can cause CNS toxicity, including seizures, depressed mental status, or leukoencephalopathy. Calcineurin inhibitors can cause seizures or other CNS toxicity.
10. **Marrow aplasia**. Severe neutropenia, thrombocytopenia, and anemia, is expected to occur for a period of 7 to 42 days following infusion of marrow. Transfusion of platelets and red blood cells is expected as supportive care. Transfusion of blood products may be associated with acquisition of HIV or a hepatitis virus. Neutropenia may increase the risk for acquiring serious infection. Thrombocytopenia may increase the risk of life-threatening hemorrhage. Hemorrhagic or infectious complications during the expected period of aplasia may result in death.
11. **Miscellaneous**. Alopecia and sterility are expected complications of the program as a whole. Cataract development is possible after TBI and/or steroids. Deficiencies of growth hormone, thyroid hormone, and sex hormones are possible after TBI. Calcineurin inhibitors can cause transient gingival hyperplasia, tremor, seizure, hypertension, headache, dysesthesia and hirsutism. Steroid therapy can also contribute to fluid retention, easy bruising, hypertension, aseptic necrosis of bone and increased susceptibility to infection. MMF can cause spontaneous abortions and birth defects. Hospitalization during conditioning and recovery period is expected to be 5-9 weeks in duration.

APPENDIX XII: Schedule of Study Evaluations

| | Screen | Day 1 to engraftment | | | | | Days 31-100 | | | Long-Term Follow-up | | |
|-------------------------------------|--------|----------------------|--------|------------------------|----------------------|--------|----------------------|----------------------|-----------------------|-------------------------|--------|---------|
| | | daily | weekly | Day 14*** (±2 days) | Day 28 (± 3 days) | weekly | Day 56 (± 7 days) | Day 80 (± 7 days) | Day 100 (± 7 days) | 6 months (± 30 days) | 1 year | 2 years |
| Informed consent | X | | | | | | | | | | | |
| Medical history | X | | | | | | | | | | | |
| Physical exam | X | X | | | | X | | | | X | X | X |
| Performance status | X | | | | | | | X Day 80-100 | | X | X | X |
| Height/Weight | X | | | | | | | X | | | | |
| GVHD evaluation | | | X | | | X | | | | X | X | X |
| Adverse events | | X | | | | X | | | | | | |
| CBC with diff | X | X | | | | X | | | | X | X | X |
| Basic Metabolic Panel | X | X | | | | X | | | | X | X | X |
| Hepatic Function Panel | X | | | | | | | | | | | |
| | | | | | | | | | | | | |
| Viral screening including CMV PCR | | | | | | | | | | | | |
| CMV Surveillance by PCR | | | | | | | | | | | | |
| Pregnancy test | X | | | | | | | | | | | |
| EBV monitoring | | | | | | | | | | | | |
| Urinalysis | X | | | | | | | | | | | |
| EKG | X | | | | | | | | | | | |
| MUGA or echocardiogram | X | | | | | | | | | | | |
| Chest x-ray or CT | X | | | | | | | | | | | |
| PFT | X | | | | | | | | | | | |
| Bone marrow bx/asp ** | X | | | | X | | | X | | | X | |
| Chimerism – BM | | | | | X | | | X | | | X | |
| Chimerism – PB | | | | X FHCRC | X | | X | X | | X | X | X |
| IgG, IgA, IgM (as possible) | | | | | X | | X | | X | X | X | X |
| Host/donor studies (FHCRC) | | | | | | | | | | | | |
| Lymphocyte panel (as possible) | X | | | | X | | X | | X | X | X | X |
| Immunophenotypic evaluation (FHCRC) | X | | | | X | | X | | X | X | X | X |

Check Section 9: Evaluation for details. Every effort will be made to complete the 1- and 2-year evaluations as close to these dates as possible, taking into consideration patient's circumstances at these time points.

as clinically indicated *For patients who received double cord blood units

NOTE: In certain circumstances (e.g., relapse or terminal illness), study evaluations may be omitted at the physician's or PI's discretion
